### **8.3.2 Sponsor-Investigator reporting: Notifying the Actelion**

This protocol is not being conducted under an FDA investigational new drug application.

Any AE reports meeting reporting criteria obligation (serious and possibly related to Valchlor) need to be reported to Actelion immediately.

Actelion Global Drug Safety will report any safety information received from SPONSOR-INVESTIGATOR to the competent Health Authorities as per regulatory reporting requirements regarding marketed products.

Additionally, if any AE or actions taken for safety reasons are sent directly to FDA by SPONSOR-INVESTIGATOR, copy of the same notification must also be sent in copy immediately to Actelion with clear notation regarding FDA notification.

## **8.4 Unmasking/Unblinding Procedures**

This is an open-label pilot investigation. Unmasking and unblinding procedures are not applicable.

## 8.5 Stopping Rules

This investigation is of low risk to study subjects. Stopping or interruption of the study may be necessary if a significant number of participants develop an unexpectedly high incidence of contact dermatitis that cannot be managed with low potency topical steroids.

## 8.6 Medical Monitoring

It is the responsibility of the Principal Investigator to oversee the safety of the study at his/her site. This safety monitoring will include careful assessment and appropriate reporting of adverse events as noted above, as well as the construction and implementation of a site data and safety-monitoring plan (see section 10 “Study Monitoring, Auditing, and Inspecting”). Medical monitoring will include a regular assessment of the number and type of serious adverse events.

## 9 Data Handling and Record Keeping

### 9.1 Confidentiality

Information about study subjects will be kept confidential and managed according to the requirements of the Health Insurance Portability and Accountability Act of 1996 (HIPAA). Those regulations require a signed subject authorization informing the subject of the following:

- What protected health information (PHI) will be collected from subjects in this study
- Who will have access to that information and why
- Who will use or disclose that information
- The rights of a research subject to revoke their authorization for use of their PHI

In the event that a subject revokes authorization to collect or use PHI, the Principal Investigator and Investigators, by regulation, retain the ability to use all information collected prior to the revocation of subject authorization. For subjects that have revoked authorization to collect or use PHI, attempts will be made to obtain permission to collect at least vital status (long term survival status that the subject is alive) at the end of their scheduled study period.

### 9.2 Source Documents

Source data is all information, original records of clinical findings, observations, or other activities in a clinical trial necessary for the reconstruction and evaluation of the trial. Source data are contained in source documents. Examples of these original documents, and data records include: hospital records, clinical and office charts, laboratory notes, memoranda, subjects’ diaries or evaluation checklists, pharmacy dispensing records, recorded data from automated instruments, copies or transcriptions certified after verification as being accurate and complete, microfiches, photographic negatives, microfilm or magnetic media, x-rays, subject files, and records kept at the pharmacy, at the laboratories, and at medico-technical departments involved in the clinical trial.

### 9.3 Case Report Forms

All data requested on the Case Report Form (CRF) will be recorded for each participant. A standardized CRF will be generated by REDCap. All missing data will be explained. If a space on the CRF is left blank because the question was not asked, “N/D” will be recorded. If the item is not applicable to the individual case, “N/A” will be recorded. All entries will be printed

legibly in black ink. If any entry error has been made, a single straight line through the incorrect entry will be drawn and the correct data will be written above it. All such changes will be initialed and dated. Errors will not be erased or whited-out. For clarification of illegible or uncertain entries, a clarification will be printed above the item, then initialed and dated. If the reason for the correction is not clear or needs additional explanation, details to justify the correction will be neatly included.

## **Data Management**

Study data to be collected and managed using REDCap electronic data capture tools hosted at the Mayo Clinic. REDCap (Research Electronic Data Capture) is a secure, web-based application designed to support data capture for research studies, providing 1) an intuitive interface for validated data entry; 2) audit trails for tracking data manipulation and export procedures; 3) automated export procedures for seamless data downloads to common statistical packages; and 4) procedures for importing data from external sources.

## **Data Processing**

All study data will be stored and analyzed at Mayo Clinic in Florida.

## **Data Security and Confidentiality**

All source documents including clinical findings, observations or other activities will be stored in a REDCap database that will be designed by the Statistician. Access to the REDCap database will be limited to the Principal Investigator, Investigators, and Statistician.

## **Data Quality Assurance**

Once the study is completed the Principal Investigator will randomly select 3 participants and compare the data documented for each on the CRF with what is entered into the REDCap database. If there is any discrepancy, the Principal Investigator and/or Investigators will cross-reference all 20 patients to ensure accuracy.

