### 3.4 Primary Study Endpoints

The primary outcome measure of efficacy will be the percent reduction of baseline Lichen Planopilaris Activity Index (LLPAI) score after 6 months of treatment defined as follows.

- Complete response: LLPAI reduction greater than 85% from baseline score.
- Partial response: LLPAI reduction of between 25-85% from baseline score.
- Non-response: LLPAI reduction of less than 25% from baseline score.

The Lichen Planopilaris Activity Index (LPPAI) is a standardized validated quantitative measure of disease activity [12]. LPPAI score (0-10) is calculated as follows: (pruritus + pain + burning)/3 + (scalp erythema + perifollicular erythema + perifollicular scale)/3 + 2.5 (pull test) + 1.5 (spreading/2). Symptoms and signs are graded on a 4-point scale with 0 = absent, 1 = mild, 2 = moderate, and 3 =severe. Clinical progression and a positive hair pull test are graded 1=yes; 0=no.

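### The only CRF-to-database comparison of stated extent covers 3 of 20 participants, so it would usually miss transcription errors confined to one or two, and such an error in the pull test can change a response class

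*Combined protocol and SAP*

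**What the plan says.** Under Data Quality Assurance (Section 9.3), once the study is over "the Principal Investigator will randomly select 3 participants and compare the data documented for each on the CRF" with what was entered in REDCap. If anything disagrees, the investigators "cross-reference all 20 patients to ensure accuracy". If nothing disagrees in the three, the plan asks for no further comparison. Section 9.3 also describes CRFs filled in and corrected by hand in ink, which implies a transcription step into the database.

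Other controls are mentioned, but none says how many records or fields are compared with the CRF. Data Management describes REDCap in general terms, including "an intuitive interface for validated data entry" and audit trails. The Data Clarification Process covers queries once raised. Section 10.1 gives a monitor or quality reviewer access to study documents.

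Section 3.4 builds the primary endpoint from the LPPAI, whose last two terms are "2.5 (pull test) + 1.5 (spreading/2", with the coding "Clinical progression and a positive hair pull test are graded 1=yes; 0=no". The classes are "Complete response: LLPAI reduction greater than 85% from baseline score", "Partial response: LLPAI reduction of between 25-85% from baseline score" and "Non-response: LLPAI reduction of less than 25% from baseline score".

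**The concern.** The full comparison depends on a trigger that is insensitive to isolated errors. It fires only if one of the three sampled participants happens to carry a discrepancy. Yet one isolated error can matter here, because a single yes/no item carries 2.5 points of a score whose response classes are cut at 25% and 85% reduction. A 0 typed for a 1 is a valid code, so range checks at entry would not flag it, and an audit trail would record it without testing it against the CRF. Section 7.2 intends to use the response classes for comparison with published systemic treatments, so a miscounted class would reach the study's main descriptive result.

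**Working it through.** The documents give no detection probability or error rate, so there is no planned figure to reproduce.

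**1. Probability that the sample misses the errors.** Inputs: 20 participants and 3 sampled at random (Data Quality Assurance). Assumptions: k participants carry a transcription error, and the check always finds an error in a sampled participant, which favours the plan. Sampling is without replacement, so

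P(miss) = C(20−k, 3) / C(20, 3), with C(20, 3) = 1140.

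| Participants affected (k) | C(20−k, 3) | P(miss) |
|---|---|---|
| 1 | 969 | 85.0% |
| 2 | 816 | 71.6% |
| 3 | 680 | 59.6% |
| 4 | 560 | 49.1% |
| 5 | 455 | 39.9% |

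The escalation rule does not alter these figures, because it acts only after the sample has hit an error.

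**2. Size of one wrong final pull-test entry.** The entry is 0 or 1 with weight 2.5 (Section 3.4), so the final score moves by 2.5 and the percent reduction by 2.5 / baseline. Section 3.4 gives the range as 0-10, but with spreading coded 0 or 1 the formula's maximum is 3 + 3 + 2.5 + 0.75 = 9.25. The smallest possible shift is therefore 2.5/10 = 25 percentage points, or 2.5/9.25 = 27.0 on the formula as written.

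**3. Whether the class changes.** Take a baseline of 7.5: six graded items summing to 15 give 5, plus 2.5 for a positive pull test, with no spreading. The true final pull test is negative but is entered as positive.

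| True final | True reduction | Final as entered | Reduction as entered | Class |
|---|---|---|---|---|
| 4 | 3.5/7.5 = 46.7% | 6.5 | 1/7.5 = 13.3% | partial to non-response |
| 1 | 6.5/7.5 = 86.7% | 3.5 | 4/7.5 = 53.3% | complete to partial |
| 2 | 5.5/7.5 = 73.3% | 4.5 | 3/7.5 = 40.0% | partial, unchanged |

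Three general results follow from the minimum shift of 25 points:
- A true complete responder wrongly entered as positive always loses that class (at most 100 − 25 = 75%).
- A true non-responder whose final score is no worse than baseline, wrongly entered as negative, always becomes at least a partial responder (at least 0 + 25 = 25%).
- A true non-responder wrongly entered as positive stays a non-responder.

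Across all baseline and final score combinations with final no higher than baseline, weighted equally, 61% (spreading coded 0-2) to 63% (spreading coded 0-1) of final pull-test errors change the class. The equal weighting is artificial, so this is illustrative only.

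**4. Effect on the result.** One participant changing class moves a class proportion by 1/20 = 5 percentage points.

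**5. Whether a larger sample would do.** To hold P(miss) at 5% or less, the sample must be 19 of 20 if one participant is affected (1/20 = 5.0%) and 16 of 20 if two are (4×3 / (20×19) = 3.2%). Only a check of all 20 removes the sampling miss.

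**The case against.** The plan's rule is a deliberate and coherent design choice. Any discrepancy in any field triggers the full comparison, so widespread transcription problems are much more likely to be caught than isolated ones. The miss probabilities apply to an error in any field, while the consequence described belongs to the heaviest single field. The documents do not allow the likelihood of the two together to be estimated. That stands, and it limits how much weight the point can carry.

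The consequence is also modest for an exploratory single-arm pilot. Moving from 10/20 (exact 95% interval 27-73%) to 11/20 (32-77%) lies well within the sampling uncertainty, and no decision in the documents turns on 5 points. That stands too.

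A reader might infer more than the documents support in three ways:
- **That this is the only data check.** It is not. Section 9.3 also requires missing data to be explained and corrections to be initialled, and the REDCap features, query process and monitoring access are further controls. What can be said is that no other comparison with the CRF has a defined extent.
- **That a wrong pull-test entry necessarily changes the class.** It does not. The partial class is 60 points wide, and the third example above stays inside it.
- **That the same 25-point minimum applies to an error at baseline.** It does not, because the denominator changes as well. With baseline 9.25 and final 2, the reduction is 7.25/9.25 = 78.4%. With the baseline pull test wrongly entered as negative (6.75), it is 4.75/6.75 = 70.4%, an 8-point shift within the same class.

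**Conclusion.** The point holds as a low-cost improvement and not as an error in the plan. The 85%, 72% and 49% miss probabilities are exact, given that errors affect one, two or four of 20 participants. That condition is an assumption. A final pull-test transcription error shifts the percent reduction by at least 25 points (27 if the formula's 9.25 maximum is used) and can change a class, with 5 points on the class proportion for each participant affected. The documents do not support a claim that such errors are present or likely. The point also assumes that LPPAI components, and not only a total, are transcribed: Section 3.7 lists the score without saying which.

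**What to change.** Before analysis, compare the LPPAI fields used for the primary endpoint with the CRF for all 20 participants. Section 3.4 uses baseline and 6 months, so this means the baseline and Week 24 visits; Week 12 is not needed. With eight components (six graded items, pull test and spreading) this is 20 × 2 × 8 = 320 values. If only the total is recorded, it is 20 × 2 = 40. Keep the 3-participant sample with escalation for all other fields.

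The cost is a few hours of existing staff time (an estimate, not a figure from the documents), with no new visits or procedures. The check has one limit that should be stated: Section 3.7 makes the CRF the source for the LPPAI score, so a value recorded wrongly on the CRF would pass even a full comparison.

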## **Data Clarification Process**

For any data query the Principal Investigator and Investigators will meet to clarify the data queried and make corrections based on consensus.

## **9.4 Records Retention**

The sponsor-investigator will maintain records and essential documents related to the conduct of the study. These will include subject case histories and regulatory documents.

The sponsor-investigator will retain the specified records and reports for;

1. Up to 2 years after the marketing application is approved for the drug; or, if a marketing application is not submitted or approved for the drug, until 2 years after shipment and

delivery of the drug for investigational use is discontinued and Actelion has been so notified. OR

2. As outlined in the Mayo Clinic Research Policy Manual –“Retention of and Access to Research Data Policy” and as outlined in the Actelion Investigator Initiated Study Agreement.

## **10 Study Monitoring, Auditing, and Inspecting**

### **10.1 Study Monitoring Plan**

The investigator will allocate adequate time for such monitoring activities. The Investigator will also ensure that the monitor or other compliance or quality assurance reviewer is given access to all the study-related documents and study related facilities (e.g. pharmacy, diagnostic laboratory, etc.), and has adequate space to conduct the monitoring visit.

### **10.2 Auditing and Inspecting**

The investigator will permit study-related monitoring, audits, and inspections by the IRB, the sponsor, and government regulatory agencies, of all study related documents (e.g. source documents, regulatory documents, data collection instruments, study data etc.). The investigator will ensure the capability for inspections of applicable study-related facilities (e.g. pharmacy, diagnostic laboratory, etc.).

Participation as an investigator in this study implies acceptance of potential inspection by government regulatory authorities and applicable compliance offices.

## **11 Ethical Considerations**

This study is to be conducted according to United States government regulations and Institutional research policies and procedures.

This protocol and any amendments will be submitted to a properly constituted local Institutional Review Board (IRB), in agreement with local legal prescriptions, for formal approval of the study. The decision of the IRB concerning the conduct of the study will be made in writing to the sponsor-investigator before commencement of this study.

All subjects for this study will be provided a consent form describing this study and providing sufficient information for subjects to make an informed decision about their participation in this study. This consent form will be submitted with the protocol for review and approval by the IRB for the study. The formal consent of a subject, using the Approved IRB consent form, must be obtained before that subject undergoes any study procedure. The consent form must be signed by the subject or the subject’s legally authorized representative, and the individual obtaining the informed consent. This study will not include vulnerable study populations.

## 12 Study Finances

### 12.1 Funding Source

This investigator initiated study is funded by Actelion Pharmaceuticals.

### 12.2 Conflict of Interest

Any study team member who has a conflict of interest with this study (patent ownership, royalties, or financial gain greater than the minimum allowable by their institution, etc.) must have the conflict reviewed by a properly constituted Conflict of Interest Committee with a Committee-sanctioned conflict management plan that has been reviewed and approved by the study sponsor-investigator prior to participation in this study.

No financial conflicts of interested are anticipated for this study.

### 12.3 Subject Stipends or Payments

No payment is given to study participants.

## 13 Publication Plan

The primary responsibility for publication of the study results is with the Primary Investigator. After the completion of study and prior to publication, the study results will be shared with Actelion Pharmaceuticals. The study will be registered at ClinicalTrials.gov prior to subject recruitment along with the posting of the results within 12 months of final data collection for the primary outcome measure.

## 15 Attachments

None
